^d See Appendix 15.3. The subject should be asked to rate his/her maximal breathlessness at pre-ISWT (-15 and 0 minutes prior to activity inducement of PAH symptoms) and immediately at the end of the ISWT (within 1 minute of completing the activity). Assessments will be recorded in the subject's source documents and eCRF.

^e Assessed at pre-ISWT (-15 and 0 minutes prior to activity inducement of PAH symptoms), at the end of the ISWT (within 1 minute of completing the activity), every minute for the first 5 minutes of the recovery, followed by every 5 minutes for the remainder of the 30-minute recovery. Assessments will be recorded in the subject's source documents and eCRF. Assessments will be performed in the following order: 1) PGI-S global PAH question; 2) PGI-S shortness of breath question; 3) PGI-S physical fatigue question. PGI-S assessments are to be conducted prior to the Borg dyspnea score assessments.

^f Pulse oximetry to be performed continuously. Pulse oximetry will include the collection of SpO₂ and HR. Pulse oximetry will start at the beginning of pre-ISWT (15 minutes prior to the ISWT) and will be continuous through the end of recovery of each individual period. The SpO₂ and HR measures obtained at -15 and at 0 minutes (prior to activity), every minute during the ISWT, every minute for the first 5 minutes of the recovery, followed by every 5 minutes for the remainder of the 30-minute recovery will be recorded in the subject's source documents and eCRF.

^g All AEs will be documented from time of informed consent until the subject discontinues or subject completes the study.

^h Subjects will be provided at least a 1-hour period for rest between ISWTs (until subject feels they are rested enough to perform again at their baseline level) prior to Period 2 assessments. The start and end times for this period should be documented in subject's source documents and eCRF.

ⁱ Includes PAH history and WHO Functional Class. Any significant changes to the subject's medical condition must be documented throughout the course of the study.

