4 SUBJECT ELIGIBILITY

4.1 INCLUSION CRITERIA

Subjects who meet the following criteria may be included in the study:

1. Subject voluntarily gives informed consent to participate in the study.
2. Males and females aged 18 years and above at the time of informed consent.
3. Established primary diagnosis of PAH that is either idiopathic or familial PAH (WHO Group 1), collagen vascular disease associated PAH, PAH associated with human immunodeficiency virus (HIV) infection, PAH induced by anorexigens/toxins, or PAH associated with repaired congenital systemic-to-pulmonary shunts (repaired ≥ 1 years).
4. Subject is deemed WHO Functional Class I, II, or III.
5. Subject has shortness of breath upon exertion (exhibits a ≥ 1 -point change in Borg dyspnea score) as assessed by the ISWT and a minimum completion of 3 shuttles (30 meters) of the ISWT. Subject may have other symptoms as well.
6. Subject is on stable dose of all FDA-approved PAH treatments (exceptions are anticoagulants and diuretics) for at least 60 days prior to Screening.
7. In the opinion of the Investigator, the subject can communicate effectively with study personnel, and is considered reliable, willing, and likely to be cooperative with protocol requirements.

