7.1 SCREENING PERIOD (STUDY DAYS -14 TO -1)

A window of up to 14 days is permitted to enroll a subject after Screening. When feasible, Screening assessments should be completed on the same day. Rescreening will be allowed with the Sponsor's Medical Monitor approval. The following assessments for Screening are required prior to initiating the Screening pre-ISWT assessments:

- Informed consent
- Demographics
- Medical history, including PAH history and WHO Functional Class
- AEs (documented from time of informed consent)
- Concomitant medications
- Vital signs (SBP and DBP)
- Assess subject eligibility per inclusion/exclusion criteria

If eligible after the above assessments, the pre-ISWT, ISWT, and ISWT recovery assessments will be conducted. Any significant changes to the subject's medical condition must be documented throughout the course of the study.

7.1.1 *Pre-ISWT*

AEs and concomitant medications will be assessed throughout the study.

The following assessments are required at -15 and 0 minutes prior to activity induction of PAH symptoms:

- PGI-S questions measurements (to be conducted prior to Borg dyspnea score assessment)
- Borg dyspnea score measurement

Pulse oximetry will be started 15 minutes prior to initiating the ISWT and will be performed continuously through the end of recovery during Period 1. The SpO₂ and HR measurements obtained at -15 and 0 minutes (prior to activity) will be recorded in the subject's source documents and eCRF. Subjects receiving supplemental oxygen during the Screening assessment must continue to receive the same flow rate at all subsequent ISWTs. The supplemental oxygen flow rate must be recorded for each activity, as applicable.

Supplemental oxygen therapy must not be introduced for subjects after the Screening assessment, unless there is an urgent medical need in the clinical judgement of the Investigator.

7.1.2 *ISWT*

AEs and concomitant medications will be assessed throughout the study.

The ISWT will be initiated and the following assessments will be performed immediately at the end of the test (within 1 minute of completing):

- PGI-S questions measurements (to be conducted prior to Borg dyspnea score assessment)
- Borg dyspnea score measurement

Pulse oximetry will be performed continuously through the ISWT. The SpO₂ and HR measurements obtained every minute during the ISWT will be recorded in the subject's source documents and eCRF.

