6.13.4 Test-retest Reliability

Test-retest reliability will assess the stability of the PGI-S items using data from subjects collected at Baseline. During this 15-minute time interval, subjects are expected to remain relatively stable. The “test” data will be PGI-S item scores at -15 minutes pre-ISWT, and the “retest” data will be PGI-S item scores at 0 minutes pre-ISWT.

Because the PGI-S items are categorical, weighted kappa coefficients will be computed (Streiner and Norman, 1995). Kappa statistics can range from -1 to 1 and are interpreted such that ≤ 0 is poor, >0 to 0.2 indicates slight agreement, 0.21 to 0.4 indicates fair agreement, 0.41 to 0.6 indicates moderate agreement, 0.61 to 0.80 indicates substantial agreement, and 0.81 to 1.00 indicates almost perfect agreement (Landis and Koch, 1977).

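### The only planned agreement coefficient for the PGI-S items uses ratings 15 minutes apart, so it cannot separate recall from reliability; longer-interval resting ratings are collected but never paired.

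*SAP*

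**What the plan says.** SAP 6.13.4 defines one retest pair. The test "data will be PGI-S item scores at -15 minutes pre-ISWT", and the retest "data will be PGI-S item scores at 0 minutes pre-ISWT". The interval is defended in one sentence: "During this 15-minute time interval, subjects are expected to remain relatively stable". The statistic is named ("weighted kappa coefficients will be computed"), but the weights are not given, nor is the visit or period that supplies the pair. The result is read against verbal bands, including "0.41 to 0.6 indicates moderate agreement, 0.61 to 0.80 indicates substantial agreement, and 0.81 to 1.00 indicates almost perfect agreement". Table 14.2.3.4 is the only reliability table in SAP section 11.

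The same resting ratings are taken three times per subject: at Screening and before each of the two Day 1 walks. Protocol Table 3-1, footnote e, has the items "Assessed at pre-ISWT (-15 and 0 minutes prior to activity inducement of PAH symptoms" and fixes their order. Screening may come well before Day 1: "A window of up to 14 days is permitted to enroll a subject after Screening". PAH treatment must have been at a stable dose "for at least 60 days prior to Screening" (Protocol 4.1).

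Two other passages bear on repeatability. Protocol 10.3.2 and SAP 6.9 both promise test-retest assessments in Cohort B. SAP 6.11.2 compares Cohort B Periods 1 and 2 on change from baseline at the end of the walk, using differences, correlations between periods, variability measures and period effects.

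**The concern.** A retest interval has to be short enough that the subject has not changed and long enough that the first answer does not simply carry over. SAP 6.13.4 argues only the first half. Conditions here favour carry-over: three single items, five response categories, a fixed order, no activity in between, and symptoms that SAP 6.13.2 expects to be at their lowest. Repeating the earlier answer takes little effort.

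If some subjects do so, kappa measures a mixture of recall and reliability, and the planned data cannot separate the two. The verbal label would still be attached without qualification.

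This matters because psychometric properties are the primary objective, and Protocol 1.2 proposes the items as endpoints for episodic symptoms in clinical studies. A 15-minute coefficient says little about whether a subject in the same resting state would give the same answer on another occasion.

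**Working it through.** The plan states no expected kappa, no precision for kappa and no recall share, so there is no planned figure to reproduce. The one sizing figure (SAP section 4) concerns the CI for a mean change and has no bearing here.

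**1. Effect of recall on kappa.** Weighted kappa is 1 - Do/De, where Do is the observed and De the chance-expected weighted disagreement. Let a share m repeat the first answer (disagreement 0) and let the rest re-rate with true kappa k (disagreement (1 - k)De). With equal margins De is unchanged, so

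observed kappa = 1 - (1 - m)(1 - k) = m + (1 - m)k, whatever the weights.

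Both m and k are assumptions.

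| True k | m = 10% | 20% | 30% | 40% | 50% |
|---|---|---|---|---|---|
| 0.41 | 0.47 | 0.53 | 0.59 | 0.65 | 0.70 |
| 0.50 | 0.55 | 0.60 | 0.65 | 0.70 | 0.75 |
| 0.60 | 0.64 | 0.68 | 0.72 | 0.76 | 0.80 |

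- From 0.50, the substantial band (0.61) is reached at m = (0.61 - 0.50)/(1 - 0.50) = 22%.
- A rise of a full 0.20 needs m = 0.20/(1 - k): 34% at k = 0.41, 40% at 0.50, 50% at 0.60.
- At m = 10% the rise is 0.10 x (1 - k), which is 0.07 at k = 0.30 and 0.03 at k = 0.70.

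**2. Does another planned analysis fill the gap?**

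| Planned analysis | Ratings used | Agreement at rest across occasions? |
|---|---|---|
| SAP 6.13.4 | Resting, 15 minutes apart | No, one baseline only |
| SAP 6.11.2, Cohort B | Post-exercise change, Period 1 v 2 | No, differences and correlations |
| SAP 6.3.2, 6.13.1, 6.13.2 | Resting average as baseline, in correlations and in distributions by visit | No pairing |

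**3. What is available.** Protocol 5.2 plans equal cohorts, so Cohort B has about 40/2 = 20 enrolled and 36/2 = 18 evaluable subjects. Cohort B is the cleaner source, because in Cohort A the two Day 1 baselines differ by design in time since dose. Between the Period 1 and Period 2 0-minute ratings each item is asked 12 more times: once at the end of the walk, 5 times in minutes 1-5, 5 times in minutes 10-30, and once at -15 minutes of Period 2. Simple repetition of the Period 1 resting answer is therefore less likely.

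**4. What longer-interval kappas might look like.** Assume resting margins of 55/30/12/2/1% or 40/35/18/5/2% and a recall-free latent correlation of 0.7.

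- Recall-free kappa is 0.46 with linear weights and 0.60-0.62 with quadratic weights. For the second set of margins (0.46 v 0.62) the choice of weights alone changes the label.
- If true change cuts the correlation by 10-30%, kappa falls to 0.29-0.40 (linear) or 0.40-0.56 (quadratic).
- With the first margins and no such change, the 95% sampling range at 18 pairs is 0.08-0.75 (linear) or 0.11-0.85 (quadratic). At 36 pairs it is 0.21-0.67 or 0.28-0.80.

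**The case against.** The strongest defence is that the items ask about severity at the moment of asking and the symptoms are episodic. For a momentary state, a longer gap trades recall for true change, and 60 days on stable doses does not show that resting symptoms are the same up to 14 days later. The documents also fix no dose timing at Screening. Low agreement across visits could therefore not be read as unreliability. This stands, and it is why the 15-minute kappa should be kept and the longer-interval values read beside it.

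Second, SAP 6.11.2 is a retest analysis of activity-induced symptoms, which are what the study is about. That also stands. It would be wrong to infer that all repeatability evidence rests on the 15-minute pair. But correlations and mean differences of change scores do not measure agreement at rest, and a correlation can be high despite a systematic shift.

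Third, no decision hangs on kappa: SAP 6.10 plans no hypothesis testing, and the bands are a descriptive guide. This limits the weight of the point but does not remove it.

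Three stronger readings are tempting and unsupported:

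- *Recall inflates kappa by a full label.* The documents give no recall share, and 20% recall leaves a true 0.50 in the moderate band.
- *The Screening and Day 1 resting ratings go unused.* They serve as baselines and enter the correlations and distributions; they are only not paired across visits or periods.
- *The longer-interval and 15-minute kappas are lower and upper bounds.* A simulation used the first margins above, 19 between-visit pairs against 36 independently drawn 15-minute pairs, correlation 0.7 cut by 10-30% between visits, and recall of 0-30%. The supposed lower bound exceeded the upper one in about 5% to 38% of runs.

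**Conclusion.** The point holds as a cheap improvement to the analysis, not as an error that invalidates it. The only agreement coefficient planned cannot distinguish recall from reliability and can be biased upwards. That follows from the design and does not depend on any particular recall share.

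The size does depend on that share. For a true kappa of 0.50 the rise is 0.05 at 10% recall, 0.10 at 20% and 0.15 at 30%. These figures assume equal margins and exact repetition by the recalling subjects. The sampling ranges above are wider than most of these shifts, so a label on the 15-minute kappa alone would be insecure for that reason as well.

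The data for a longer-interval check already exist and no planned analysis uses them in that way.

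**What to change.** In SAP 6.13.4 and Table 14.2.3.4:

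1. Keep the 15-minute weighted kappa, and state which visit or period supplies the pair.
2. State the weights, and use the same ones throughout.
3. Add weighted kappa with 95% CI in Cohort B for the 0-minute resting ratings: Screening v Day 1 Period 1, and Day 1 Period 1 v Period 2.
4. Show the 15-minute kappa within Cohort B too, so that the values refer to the same subjects.
5. Interpret the values together: the 15-minute value may be raised by recall and the longer-interval values lowered by true change. Do not attach the verbal label to the 15-minute value alone, and do not call the values bounds.

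The added rows would also give the Cohort B test-retest promise in Protocol 10.3.2 and SAP 6.9 an agreement measure. The cost is some SAP wording and a few table rows per item, with no new data or visits. The downsides are wide intervals from about 18-20 pairs and a Screening comparison that mixes in uncontrolled dose timing; both should be stated in the table footnote.

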6.13.5 Responsiveness to Change

It is important to provide evidence regarding the responsiveness of the PGI-S items—that is, their ability to detect change when change is expected. The responsiveness of the PGI-S items will be evaluated by computing effect-size estimates of change for each PGI-S item as the mean change from the first time point to the second time point divided by the standard deviation at the first time point. In addition, the observed score changes and associated t-tests (p-values) will be tabulated. Baseline (pre-ISWT -15 minutes and 0 minutes) to 0 minutes post-ISWT will be examined, as will 0 minutes post-ISWT to 30 minutes post-ISWT (end of recovery period).

Cohen (1992) provides a general rule of thumb for the interpretation of effect-size estimates: effect sizes of approximately 0.20 represent small effects, those of approximately 0.50 represent moderate effects, and those greater than approximately 0.80 represent large effects.

7 ANALYSIS OF SAFETY

The safety assessments will consist of AEs including serious adverse events (SAEs), and vital signs.

All safety analyses will be based on the Safety Population. No formal inferential testing will be reported for routine safety analyses.

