The baseline PGI-S and Borg dyspnea score assessments will be conducted prior to (-15 and 0 minutes; pre-ISWT) an activity that is typically expected to induce symptoms of PAH. The subject will initiate activity (ISWT; Appendix 15.2), and these same assessments will be performed immediately at the end of the ISWT (within 1 minute of completing the activity). The PGI-S assessments will also be performed throughout recovery following completion of the ISWT. Continuous pulse oximetry will be performed at each clinic visit starting at each Baseline and through recovery.

Vital sign assessments will be performed at the beginning and at the end of each clinic visit. On Day 1, subjects will be provided rest (at least 1 hour) between the 2 ISWTs. Vital sign assessments will be performed at the beginning and at the end of each clinic visit.

All AEs will be documented from the time of informed consent until the time screen failure is documented, the subject discontinues, or the subject completes the study.

The study will consist of the following periods:

Screening: During the Screening Period, subjects who sign the Informed Consent Form (ICF) will first undergo all Screening assessments to evaluate eligibility as listed in the

inclusion/exclusion criteria. A window of up to 14 days is permitted to enroll a subject after Screening. When feasible, Screening assessments should be completed on the same day. Rescreening will be allowed with the Sponsor's Medical Monitor approval.

During Screening, the ISWT will be performed to determine eligibility and the ability to induce symptoms. Completion of a minimum of 3 shuttles (30 meters) of the test will be required for study eligibility. Pre-ISWT, ISWT conduct, and ISWT recovery will be performed and specific assessments will be conducted as outlined below.

Pre-ISWT: Baseline PGI-S (Appendix 15.1) and Borg dyspnea score (Appendix 15.3) assessments completed at -15 and 0 minutes prior to activity induction of PAH symptoms will be performed. Continuous pulse oximetry, for the assessment of oxygen saturation and HR, will be initiated at the beginning of pre-ISWT and performed until the end of recovery from the ISWT. Vital signs (systolic blood pressure [SBP], diastolic blood pressure [DBP]) will be assessed at the beginning of pre-ISWT.

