9.2 DOCUMENTATION OF ADVERSE EVENTS

All AEs will be documented from time of informed consent until the subject discontinues or subject completes the study. An AE or SAE occurring during the study must be documented in the subject's source documents and on the appropriate eCRF page(s). Information relating to the AE, such as onset and cessation date and times, intensity, seriousness, and outcome, is also to be documented in the eCRF (see Appendix 15.4 for definitions). Where possible, AEs should be recorded using standard medical terminology. If several signs or symptoms are

clearly related to a medically defined diagnosis or syndrome, the diagnosis or syndrome should be recorded on the eCRF page, not the individual signs and symptoms.

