6 STATISTICAL METHODS

6.1 DATASETS FOR ANALYSES

This study has the following analysis populations:

- All Subjects (All): Subjects who consented to the study protocol.
- Full Analysis Set (FAS) Population: Subjects who enrolled in the study protocol (initiated Day 1 procedures). Tabulations for endpoint analyses will be conducted on this population.
- Per-Protocol (PPROT) Population: Subjects who completed the study protocol, do not have significant protocol deviations in the study, and were appropriately included to investigate the research hypotheses. The Sponsor will assess inclusion of this population at the time of database lock. Endpoint analyses may be conducted from this population if the population is applicable after Sponsor review.
- Safety Population: Subjects who initiated the ISWT at Screening.
- Psychometric Analysis Population (PAP): Subjects who completed the PGI-S items or Modified Borg Scale at any visit or time point.

Summary tables will be presented with the number and percentages of subjects overall and by cohort.

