7.2.2 Date of Onset of Adverse Event

The onset date of each AE will be the date recorded on the eCRF.

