11 LIST OF TABLES AND FIGURES

Table No.	Title	Population
14.1.1	Summary of Subject Accountability and Disposition	All
14.1.2	Summary of Analysis Populations	All
14.1.3	Summary of Demographic and Baseline Characteristics	All
14.1.4	Summary of Medical and Surgical History	All
14.1.5.1	Summary of Prior Medications	All
14.1.5.2	Summary of Concomitant Medications	All
14.1.6	Summary of Protocol Deviations	All
14.2.1.1	Summary of PGI-S Change from Baseline	All
14.2.1.2	Summary of PGI-S Change from Baseline	PPROT
14.2.1.3	Figures for PGI-S Change from Baseline	FAS
14.2.1.4	Figures for PGI-S Change from Baseline	PPROT
14.2.1.5	Summary of PGI-S Time to Recovery	FAS
14.2.1.6	Summary of PGI-S Time to Recovery	PPROT
14.2.2.1	Summary of Borg Change from Baseline	All
14.2.2.2	Summary of Borg Change from Baseline	PPROT
14.2.2.3	Summary of Pulse Oximetry and Heart Rate	All
14.2.2.4	Summary of Pulse Oximetry and Heart Rate	PPROT
14.2.2.5	Figures for Pulse Oximetry and Heart Rate	FAS
14.2.2.6	Summary of ISWT	All
14.2.3.1	PGI-S Response Frequency (%) Distributions	PAP
14.2.3.2	PGI-S Construct Validity Correlations	PAP
14.2.3.3	PGI-S Known-Groups ANOVAs	PAP
14.2.3.4	PGI-S Test-retest Reliability	PAP
14.2.3.5	PGI-S Responsiveness	PAP
14.3.1.1	Summary of Treatment-emergent Adverse Events by System Organ Class and Preferred Term in Decreasing Order	Safety
14.3.1.2	Summary of Treatment-emergent Adverse Events by Preferred Term in Decreasing Order	Safety
14.3.1.3	Summary of Serious Treatment-emergent Adverse Events by System Organ Class and Preferred Term in Decreasing Order	Safety
14.3.1.4	Summary of Treatment-emergent Adverse Events by Severity by System Organ Class and Preferred Term in Decreasing Order	Safety
14.3.1.5	Summary of Treatment-emergent Adverse Events Leading to Study Discontinuation by System Organ Class and Preferred Term in Decreasing Order	Safety

14.3.2.1	Listing of Deaths	Safety
14.3.2.2	Listing of Serious Adverse Events	Safety
14.3.3	Summary of Vital Signs	Safety

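### The listings of deaths and SAEs are limited to subjects who began the Screening walk, so an event after consent that prevents the walk is in no planned safety table or listing

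*SAP*

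**What the plan says.** **Collection.** Protocol 9.2 states: "All AEs will be documented from time of informed consent until the subject discontinues or subject completes the study". Protocol 3.1 adds screen failure as an end point: "All AEs will be documented from the time of informed consent until the time screen failure is documented". SAP 3.1 repeats that window. Adverse events are thus meant to be collected in people who never pass screening.

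**Analysis.** SAP 6.1 defines the "Safety Population: Subjects who initiated the ISWT at Screening". SAP section 7 states: "All safety analyses will be based on the Safety Population". In SAP section 11 every output numbered 14.3 carries the population label Safety. This includes the listing of deaths (14.3.2.1) and the "Listing of Serious Adverse Events" (14.3.2.2).

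**Order of events at Screening.** Protocol 7.1 puts consent, demographics, history, adverse events, medications, vital signs and an eligibility check before the walk, which follows only if the subject is still eligible. On timing it says: "When feasible, Screening assessments should be completed on the same day".

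**Onset.** SAP 7.2.1 defines a treatment-emergent event (TEAE) by reference to the first ISWT, and leaves events that start before it out of the summaries. SAP 7.2.2 states: "The onset date of each AE will be the date recorded on the eCRF". Protocol 9.2 has sites record in the eCRF details "such as onset and cessation date and times, intensity, seriousness, and outcome".

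**The concern.** Data collection opens at consent, but the safety outputs open at the first step of the Screening walk. Between the two, entry to the Safety Population can depend on the event itself: a subject who dies, or whose SAE stops the walk, is left out because of that event. Limiting TEAE tables to people who underwent the symptom-inducing procedure is sensible. Limiting the lists of deaths and SAEs in the same way is not, because those lists are meant to account for every such event that was collected.

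The stake is a mismatch in the study report. Under Protocol 9.4 the sponsor would receive such an SAE within 24 hours, yet a report that follows the SAP exactly would not list it. Adverse events are one of the two stated bases of the safety objective (Protocol 2.3, SAP 2.3).

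**Working it through.** The plan states no figure on this point, so there is none to reproduce. The check follows three kinds of subject through the rules.

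1. **Event after consent, no walk.** The event is collected (Protocol 3.1 and 9.2). The subject did not begin the Screening ISWT and so is outside the Safety Population (SAP 6.1). The event is in none of tables 14.3.1.1 to 14.3.1.5 and in neither listing 14.3.2.1 nor 14.3.2.2. The subject is counted in Table 14.1.1 (population All), with a reason for discontinuation at most (SAP 6.5). A drug given for the event could appear in Table 14.1.5.2 (All). Neither table lists the event as a death or SAE.
2. **Event after consent, then a walk.** The subject joins the Safety Population. An SAE is in listing 14.3.2.2 and, because it began before the first ISWT, is left out of the TEAE summaries (SAP 7.2.1).
3. **Event after the walk has begun, including in a subject who then fails screening.** The subject is in the Safety Population, and the listings cover the event.

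Only the first case is lost.

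**Rough size.** The documents give neither an SAE rate, nor the number consented, nor the time from consent to walk. The following values are assumptions:

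- 45 to 60 consented subjects (about 40 are to be enrolled);
- 0.2 to 0.8 SAEs per subject-year;
- a gap of 1 to 13 days, the longest that Days -14 to -1 allow.

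Expected SAEs between consent and walk = subjects with a gap × gap in days / 365 × yearly rate.

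- Low: 45 × 1/365 × 0.2 = 0.02.
- A tenth of 60 subjects waiting the full 13 days, at the high rate: 60 × 0.10 × 13/365 × 0.8 = 0.17.

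Both results count every SAE in the gap. Only those that stop the walk are omitted, so the relevant number is lower.

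**Onset and walk.** SAP 7.2.1 covers events after the first ISWT and excludes those starting before it; an event that begins during the walk fits neither description. SAP 7.2.2 names a date and is silent on time. The data to settle the order appear to be collected: onset time under Protocol 9.2, and an ISWT start time used in a derivation in SAP 6.12.3.

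**The case against.** **The population choice is coherent.** No investigational drug is given, the walk is the procedure that provokes symptoms, and before it subjects have only history, vital signs, oximetry and questionnaires. This stands for the TEAE tables, and the fix leaves them alone. It does not explain why the two listings should be cut in the same way when collection deliberately starts at consent.

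**Other outputs and promises cover the gap.** Disposition and concomitant medication are tabulated for all consented subjects, SAEs go through 24-hour reporting, and Protocol 10.6 promises that all relevant data will be presented. A reader might therefore infer that such an event would vanish from every output, and the documents do not support that: the subject remains in disposition. But none of these routes lists the event as a death or SAE. Expedited reporting is not an analysis output. Protocol 10.6 names no listing or population, and the SAP states that it supersedes the protocol's statistical considerations. It may be said that SAP section 11 is not a full inventory of data listings. Still, it does name these two, and it gives their population.

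**The numbers could be made to look large.** If all 60 subjects waited 13 days at the high rate, the formula gives 60 × 13/365 × 0.8 = 1.71. That is not a realistic bound. Protocol 7.1 prefers same-day screening, names no pre-walk test with a turnaround time, and describes the 14 days as time to enroll after Screening, which falls mainly between Screening and Day 1.

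**Same-day events.** A reader might infer from SAP 7.2.2 that events on the day of the walk cannot be ordered against it. The documents do not support this. The TEAE rule refers to the walk, not to a calendar date; SAP 7.2.2 only says where the onset date comes from; and times are recorded. What remains is a missing instruction to use the time.

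**Conclusion.** The point holds as a gap in completeness. Applied exactly, the SAP leaves out of every planned safety table and listing a death or SAE that occurs after consent and prevents the Screening walk. This follows from the definitions and needs no assumption about rates.

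The expected number of such events is small. Under the assumptions shown it is about 0.02 to 0.17 SAEs of any kind in the gap, and fewer that stop the walk; the documents do not quantify it. No primary or psychometric result is affected. The change is still worth making, because one unlisted death or SAE would be a material omission and the correction is very cheap. The onset wording is a minor clarification and does not carry the point.

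**What to change.** - In SAP section 11, assign listings 14.3.2.1 and 14.3.2.2 to the existing All population (consented subjects), with a flag for onset before the first ISWT. In SAP section 7, state that these two listings are the exception to the Safety Population rule.
- Keep tables 14.3.1.1 to 14.3.1.5 on the Safety Population.
- As a clarification in SAP 7.2.1 and 7.2.2, say that TEAE status is set by recorded onset date and time against the start time of the first ISWT, so that events beginning during the walk are counted. The sponsor should confirm that the start time is captured for the Screening walk.

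The cost is two population labels, one flag and a sentence or two in the SAP. No new data collection is evident. The downside is that a few events unrelated to the walk may be listed; the flag identifies those that began before it.
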